5. STUDY POPULATION

5.1 Selection of the Study Population

Up to 1,000 male and female participants, adults ≥ 18 years of age and children < 18 years of age, will be screened to enroll participants who meet all eligibility criteria and agree to participate.

Patients will be recruited from 10 VTEU sites and/or their sub-sites. Sites can enroll from either outpatient or inpatient sites, or both. Enrollment will be stratified by disease severity or other major categories of disease presentation as applicable. Pregnant women will not be excluded from enrollment. Blood collection volumes will be adjusted accordingly for these participants. There will not be a required sample size for this population. As this study is a descriptive study, sample size is based on feasibility instead of power for hypothesis testing.

- Group 1: Patients with confirmed or suspected Pathogen “X” infection, and
- Group 2: Close contacts of patients with confirmed and/or suspected Pathogen “X” infection enrolled in Group 1.

A subset of 10-20 adult volunteers from Group 1 will undergo leukapheresis during follow-up to compare immunological responses in those with variable severity and also to allow future comparisons with those receiving Pathogen “X” vaccines (enrolled in other studies). Study staff will inform potential participants/legally authorized representatives (LAR) of the study, obtain informed consent, and determine study eligibility. Individuals who meet all study eligibility criteria and agree to participate will be enrolled.

Usual clinical management at VTEU outpatient or inpatient sites, including standard medical care and standard therapy, will not be modified because of the study. All participants will receive appropriate treatment for Pathogen “X” that is accepted by medical experts as standard of care for the specific institution and is widely used by healthcare professionals.

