7. STATISTICAL CONSIDERATIONS

7.1 Study Hypotheses and Design

The overall objective of this prospective observational cohort study is to characterize the natural history and immune responses to Pathogen “X” infection in patients who present varying levels of disease severity and clinical symptoms, and in their close contacts. The study hypothesizes that Pathogen “X” elicits broad immune responses in individual patients, and that these responses vary over time during infection and as disease severity and symptoms progress. The study will determine whether immune responses associated with disease severity, symptoms, and demographic variables. In particular, it will focus on association with age, and consider other known or suspected factors that associate with immune responses (e.g., sex). It will also characterize spread of infection among close contacts of Pathogen “X” infected patients.

To address its objectives with adequate power, the study will target enrolling approximately 1,000 Pathogen “X” infected or suspected children and/or adult patients (Group 1) and children and/or adult close contacts of the Pathogen “X” infected patients who are enrolled in Group 1 (Group 2). Participants in Group 1 will be representative of the Pathogen “X” disease spectrum.

The primary statistical analysis of data from participants enrolled in Group 1 will be conducted using the most severe level of care (hospitalized ICU, hospitalized non-ICU, outpatients not hospitalized) received by each study participant. Secondary statistical analyses will be performed using additional disease severity scales if developed (see Appendix B).

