7.2.1 Power Analysis for Continuous Outcome Variables

Some statistical analyses will characterize immune responses at a given time point based on continuous outcome variables (e.g., response magnitude of Pathogen “X” specific B cells) by estimating the mean response magnitude in different groups of patients. The precision with which a mean response magnitude (more generally, the mean of a continuous outcome

variable) is estimated may be evaluated by constructing an associated two-sided 95% confidence interval. The width of these intervals is independent of the mean response magnitude but depends on the observed standard deviation of the response magnitude measurements. The half-widths of confidence intervals are reported in Table X for multiple values of the standard deviation and several group sizes [provide examples of group sizes]. The calculations assumed independent and identically normally distributed observations. [discuss results presented in table].

Table X: Half-width of two-sided 95% confidence intervals for the mean of a continuous outcome measure based on observing a particular standard deviation as a function of the sample size (n) and the observed standard deviation

std. dev.	sample size (n)					
0.10						
0.25						
0.50						
0.75						
1.0						
2.0						
5.0						
10.0						

We also evaluated the power of the study to detect statistically significant differences when comparing mean response magnitudes between two independent groups. The calculations assumed a nonparametric two-sided Wilcoxon rank sum test with a 5% significance level, and that observations are sampled from two independent and normally distributed populations. The power of the test is presented in Table X as a function of the standardized (i.e., Cohen's) effect size and of the sample sizes (n1 and n2). [discuss results presented in table]

Table X: Power for comparison of response magnitude between 2 groups of sizes n1 and n2, respectively, as a function of the standardized (Cohen's) effect size

standardized effect size		n1							
0.25	n2								
0.50	n2								
0.75	n2								
1.00	n2								

One goal of the primary objective of the study is to determine whether continuous measures of immune responses (e.g., magnitude of binding and neutralizing antibody responses to Pathogen "X" measured in blood) associate with age. These analyses may be conducted by computing correlation coefficients between immune responses and age (or any pair of continuous variables

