Continuous variables will be analyzed using univariate and bivariate descriptive statistics to summarize data by group, time point, gender, and race, for example. Data will be visualized using graphical techniques, including boxplots, density estimates, scatterplots, heatmaps, and networks. Comparisons of two independent groups will be performed using a nonparametric Wilcoxon rank sum test. To compare more than two groups, we will first use a Kruskal-Wallis or an F-test (depending on the normality assumption) to test for overall differences. Should the overall test reach statistical significance at the 2-sided 0.05 level, individual (post-hoc) pairwise tests will be performed (e.g., using Dunn’s procedure following a Kruskal-Wallis’ test). Comparisons of paired data will be accomplished using the Wilcoxon signed-rank test or paired *t*-test. In addition, since participants are not randomized between groups at enrollment, some of the statistical analyses will use multiple linear regression to compare groups while adjusting for potential confounders (e.g., age, gender, race, comorbidities). Longitudinal data will be analyzed using statistical methods for repeated measures and dependent data (e.g., mixed-effects models,¹³ generalized estimating equations (GEE).¹⁴ Similar modeling approaches will be considered to account for potential intra-close contact correlations in analyses that involve data from Group 2. Preliminary data transformations (e.g., logarithmic, square root) may be

performed in regression analyses to better satisfy assumptions of symmetry and homoscedasticity (constancy of variance).

If the frequency of missing data is substantial, statistical analyses may be performed using parametric models fitted using the method of maximum likelihood. This approach is robust when data are missing at random (MAR). MAR assumes that the probability of an observation being missing may depend upon the observed responses and observed covariates, but it does not depend on any unobserved factors. This assumption is less stringent than the missing completely at random (MCAR) assumption. If measurements of immune responses are left- and/or right-censored, we will use Hughes’ linear mixed effects models to accommodate censoring in analyses of repeated measures.¹⁵ Analyses of repeated immunogenicity measurements may be done using weighted GEE methods,¹⁶ which are valid under MAR.

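### The overall test for more than two groups is chosen on normality alone, so on the F-test branch its true error rate depends on group variances that nobody checks

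*Protocol*

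**What the plan says.** Protocol section 7.4.2 sets the rule for comparing more than two groups on a continuous variable: "we will first use a Kruskal-Wallis or an F-test (depending on the normality assumption) to test for overall differences". That test then acts as a gate: "Should the overall test reach statistical significance at the 2-sided 0.05 level, individual (post-hoc) pairwise tests will be performed". Dunn's procedure is named as an example after Kruskal-Wallis; no pairwise method is named after the F-test.

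Equal variance appears once in the section, and not for this test: data transformations are optional and are "performed in regression analyses to better satisfy assumptions of symmetry and homoscedasticity".

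The rule covers severity because section 7.1 bases the primary analysis of Group 1 on "the most severe level of care (hospitalized ICU, hospitalized non-ICU, outpatients not hospitalized) received by each study participant", which makes three groups.

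The protocol fixes neither the sizes nor the spread of those groups. Section 5.1 says "Enrollment will be stratified by disease severity or other major categories of disease presentation as applicable" but sets no target per stratum. Section 7.1 gives only an overall target, "the study will target enrolling approximately 1,000", covering Groups 1 and 2 together. Section 7.2.1 says that precision "depends on the observed standard deviation of the response magnitude measurements", but gives no SD for any severity group.

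**The concern.** The usual one-way F-test pools the within-group variances. That is harmless when the variances are equal, and nearly so when the groups are the same size. Otherwise the pooled variance is dominated by the large groups. If the small group is the most variable, the denominator is too small and the test rejects too often. If the large group is the most variable, the test rejects too rarely.

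A normality check does not detect this. Each group can be exactly normal while the SDs differ, and such data are sent to the F-test, the more exposed of the two branches.

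At stake is the gate itself. The overall result decides whether pairwise differences are examined at all. A drifting error rate therefore either opens comparisons on noise or closes them on real differences, and the reader of the result cannot tell which.

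**Working it through.** **Inputs from the protocol.** Three groups (section 7.1); nominal level 0.05, and F-test or Kruskal-Wallis chosen on normality (section 7.4.2).

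**Inputs assumed, because the protocol gives none.** Group sizes, written ICU/ward/outpatient, of 40/80/200, 50/100/190 and 60/120/180, with 100/100/100 for comparison. SD ratios in the same order of 1.5:1.25:1 and 2:1.5:1, and the reverse. Data are normal with equal means, so every F or Welch rejection is a false positive.

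**Step 1: why the F-test drifts.** Under equal means, with k = 3 groups of size nᵢ and N in total,

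- E[between mean square] = Σ(1 − nᵢ/N)σᵢ² / (k − 1)
- E[within mean square] = Σ(nᵢ − 1)σᵢ² / (N − k)

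For 40/80/200 with SDs 2:1.5:1 (variances 4, 2.25, 1):

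- Between: (0.875×4 + 0.75×2.25 + 0.375×1)/2 = 5.5625/2 = 2.781
- Within: (39×4 + 79×2.25 + 199×1)/317 = 532.75/317 = 1.681
- Ratio: 1.65, where a valid test needs 1

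Reversing the SDs gives (0.875×1 + 0.75×2.25 + 0.375×4)/2 = 2.031 over (39 + 177.75 + 796)/317 = 3.195, a ratio of 0.64. With equal sizes the ratio is exactly 1 whatever the SDs.

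**Step 2: rough size of the error.** The 5% critical value of F on 2 and 317 degrees of freedom is 3.02. With two numerator degrees of freedom and a large denominator, P(F > x) ≈ exp(−x), so the error is about exp(−3.02/ratio). A ratio of 1.65 gives exp(−1.83) = 16%; 0.64 gives exp(−4.7) = 0.9%; 1 gives exp(−3.02) = 4.9%.

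**Step 3: simulation.** 20,000 data sets per row, each tested at 0.05 (Monte Carlo standard error about 0.15 points at 5% and 0.26 at 16%). Kruskal-Wallis is referred to chi-square on 2 degrees of freedom. Welch's test weights each mean by wᵢ = nᵢ/sᵢ² and does not pool variances. The first row reproduces the nominal 5%.

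| Sizes | SDs | Ratio | exp approx. | F-test | Kruskal-Wallis | Welch |
|---|---|---|---|---|---|---|
| 40/80/200 | 1:1:1 | 1.00 | 4.9% | 4.9% | 5.0% | 5.0% |
| 40/80/200 | 1.5:1.25:1 | 1.36 | 10.8% | 11.2% | 8.0% | 5.0% |
| 40/80/200 | 2:1.5:1 | 1.65 | 16.1% | 16.4% | 10.0% | 4.9% |
| 50/100/190 | 1.5:1.25:1 | 1.29 | 9.5% | 9.7% | 7.5% | 5.0% |
| 50/100/190 | 2:1.5:1 | 1.51 | 13.5% | 13.5% | 9.0% | 4.9% |
| 60/120/180 | 1.5:1.25:1 | 1.23 | 8.5% | 8.6% | 6.8% | 4.8% |
| 60/120/180 | 2:1.5:1 | 1.39 | 11.5% | 11.9% | 8.7% | 5.2% |
| 40/80/200 | 1:1.25:1.5 | 0.75 | 1.8% | 2.0% | 2.9% | 4.9% |
| 40/80/200 | 1:1.5:2 | 0.64 | 0.9% | 1.2% | 2.1% | 4.7% |
| 60/120/180 | 1:1.25:1.5 | 0.83 | 2.6% | 2.9% | 3.6% | 5.2% |
| 60/120/180 | 1:1.5:2 | 0.74 | 1.7% | 2.3% | 3.1% | 4.7% |
| 100/100/100 | 2:1.5:1 | 1.00 | 4.9% | 5.6% | 5.7% | 4.8% |

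Shorter runs of 5,000 or 6,000 data sets put the worst row between 15.5% and 17% for the F-test, and the mildest inflated row at 8.0% for the F-test and 5.9% for Kruskal-Wallis. Hence the rounded ranges of 8-17% and 6-10%.

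**Step 4: does the normality switch protect?** If each group is tested for normality at 5%, normal data pass in all three groups with probability 0.95³ = 86%, whatever the SDs. Simulating the whole rule at 20/60/120 with SDs 2:1.5:1 gave 15.6% with a Shapiro-Wilk test in each group and 14.9% with one on pooled residuals, against 16.7% for the F-test alone and 5.0% for Welch. The switch removes little of the excess.

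**Step 5: price of Welch when variances are equal.** At 50/100/190 with means 0.45/0.20/0 SD, power was 75.5% for F against 75.0% for Welch in one run, 76.6% against 76.0% in a second, and 75.9% against 75.1% in a third: a loss of 0.5 to 0.8 points.

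**The case against.** The strongest reply is that section 7.4 calls itself an overview, that whether the F-test is classical or Welch's form is a matter for the SAP, and that Welch's ANOVA is also an F-test. Part of this stands: the word F-test does not exclude Welch, and an SAP could settle it. But the protocol does not leave the criterion open. It names normality and nothing else, and an SAP that followed it faithfully would carry the weakness forward.

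Second, sizes and SDs are assumed. That stands in full. Stratified enrollment could bring the groups close to balance, and balance removes nearly all of the problem. It is not guaranteed, because no stratum targets are set and severity is the worst level of care reached, so a participant's group can change after enrollment. Nothing in the protocol shows which group would be the more variable, so even the direction of the error is unknown.

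Third, Kruskal-Wallis is valid for its own null hypothesis of identical distributions, and section 7.4.2 speaks only of overall differences. This stands. A reader might infer from the table that both branches are faulty; the documents do not support that. The Kruskal-Wallis figures count as errors only if a significant result is reported as a shift in location.

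Fourth, section 7.2 calls the analyses mostly exploratory, and section 7.4.2 also plans covariate-adjusted regression. This limits the importance of the point but does not make the selection rule sound.

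**Conclusion.** The point holds as a modest one. Section 7.4.2 selects the overall test on a criterion that does not address the F-test's sensitivity to unequal variances. Under the assumed sizes and SD ratios, the F-test's error at a nominal 5% is about 8-17% when the smallest group is the most variable, about 1-3% when the largest group is, and about 5-6% with equal sizes. These figures assume normal data, equal means and the usual pooled-variance form of the test.

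A reader might infer that this study's severity tests will run at an error above 15%. The documents do not support that. Within the assumed range it happens only on the F-test branch, at 40/80/200 with SDs 2:1.5:1. More extreme inputs give more (30.6% at 30/100/300 with SDs 3:2:1), but nothing in the protocol points to such values, and it equally allows balanced groups or the conservative pattern. What can be said is that the level of this test is not controlled by the rule as written.

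**What to change.** In section 7.4.2, or in the SAP with a reference from it:

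- Where the F-test branch is used, specify Welch's ANOVA, followed by Games-Howell pairwise comparisons.
- Use heteroscedasticity-robust standard errors in the linear regressions that make the same group comparisons.
- Keep Kruskal-Wallis with Dunn's procedure for the other branch, and state that a significant result is reported as a difference in distribution, not as a difference in location.

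This takes a few sentences and is standard in SAS and R, the software named in section 7.4. The statistical cost is about half a percentage point of power when variances are equal (0.5 to 0.8 points in the runs above). Group sizes and enrollment are unaffected.

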4. STUDY DESIGN

This is a prospective, observational, noninterventional cohort study designed to collect clinical information and specimens to evaluate the innate and adaptive immune responses from up to 1,000 study participants. Both males and females will be screened for study interest and eligibility and enrolled, adults ≥ 18 years of age and children < 18 years of age. Two types of participants will be recruited:

- Group 1: Patients with confirmed or suspected Pathogen “X” infection, and
- Group 2: Close contacts of patients with confirmed and/or suspected Pathogen “X” infection enrolled in Group 1.

The study will ensure enrollment of patients that have clinical symptoms representative of the disease spectrum.

Group 1

Baseline data will be collected from participants with confirmed or suspected Pathogen “X” infection including demographics/sociodemographics, medical history, exposure history, medications, signs/symptoms and symptom onset date to determine the days post-illness onset (DPO). Specimens will be collected from body compartment specific to Pathogen “X”. Specimens may include whole blood, serum, urine, saliva, stool or other body fluids as available (e.g., semen, vaginal secretions, breast milk) depending on the specifics of Pathogen “X”. Specimens may be salvaged if available from standard of care testing. Clinical information and specimens will be collected at enrollment and then at an interval determined by the biologic characteristics after enrollment (up to 12 months). See Section 6 Study Procedures/Evaluations.

The association between age, severity of illness, and duration of illness on Pathogen “X” immune responses will also be explored.

An optional study visit will be conducted between DPO 30 and 90 in adult participants from Group 1 who volunteer to undergo leukapheresis. Leukocytes will be selectively harvested; red cells and other blood components will be returned to the patient. Participation will be offered to all patients and volunteers will be accepted until the spots are filled. In a typical 1½ to 3-hour leukapheresis procedure, approximately 5×10^8 to 1×10^{10} cells can be isolated with only minimal loss of red blood cells. No sedation is required. The procedure will be done by trained staff at the study site and will be done using devices and procedures that conform to standard guidelines and SOPs.

Identification of close contacts will take place as soon as possible after Group 1 participants are enrolled.

Group 2

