7.4.2 Analysis of Primary and Secondary Endpoints

The statistical analysis for the primary and secondary objectives of the study will seek to answer key questions related to the immune responses and clinical course of Pathogen “X” infection.

The study will not randomize patients between study arms. Therefore, in order to account for potential confounders, statistical analyses will either be stratified by group or seek to adjust for covariates where deemed appropriate. For example, some analyses will be stratified by study arm (e.g., Groups 1 and 2). Other analyses will be stratified or adjust for age (treated as continuous or categorical variable), sex, for example.

Categorical variables (e.g., disease severity, binary responses, participants’ characteristics at enrollment) will be analyzed by tabulating the relative frequency of each category by group and time point, as appropriate. Crude response rates will be presented with their 95% confidence interval estimates calculated using the score test.¹² Fisher’s exact tests will be used to compare response rates between two groups. Because participants enrolled in distinct groups may differ in terms of demographic variables and comorbidities, many of the statistical analyses will compare response rates between groups using binary logistic regression to adjust for potential confounders (e.g., age, gender, race, comorbidities).

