To visualize multivariate immune response variables, we may use dimensionality reduction techniques (e.g., principal component analysis, multidimensional scaling, Uniform Manifold Approximation and Projection), and perform unsupervised learning (e.g., k-means, model-based clustering) to identify subgroups of participants with similar immune profiles.

Where appropriate (e.g., in transcriptional analysis), we will perform formal p-value adjustment for multiple comparisons. We will control either the family-wise error rate (FWER) using the Holm-Bonferroni procedure¹⁷ or the false discovery rate (FDR) using the Benjamini-Hochberg or the Benjamini-Yekutieli procedures.^{18,19} The selection of a method for p-value adjustment may depend on the objective of the statistical analysis.

Some of the primary and secondary analyses will seek to identify predictive signatures of categorical outcome variables (e.g., disease severity) using a combination of demographic (e.g., age, race), clinical (e.g., comorbidity), and laboratory (e.g., viral load, immune responses) variables. We will first build candidate predictive models using multiple regression techniques (e.g., binary logistic regression for binary endpoints) modeling the probability of a particular event (e.g., disease progression, hospitalization) as a function of a set of predictors, while adjusting for potential confounding factors, as appropriate). Models may be fitted using regularization techniques (e.g., lasso, elastic net) and cross-validation to identify optimal tuning parameters. Where appropriate, we will assess the predictive power of candidate signatures using doubly (nested) cross-validated receiver operating characteristics (ROC) curves.

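### Severity comparisons at Visit 1 are not aligned on days since illness onset, and the hospitalization and progression models may use samples taken after the event

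*Protocol*

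**What the plan says.** **Timing of samples.** For Group 1, Section 4 of the protocol collects the "symptom onset date to determine the days post-illness onset (DPO"). Table 2 in Appendix A labels the scheduled follow-up visits DPO 7, 15, 30, 90, 180 and 365, and a footnote says that the days may change. Visit 1 is labelled only as Day 1, the day of enrolment (Section 6.1.1). Neither the inclusion nor the exclusion criteria (Sections 5.2.1 and 5.2.3) limit time since onset. Sites may recruit from outpatient and inpatient settings (Section 5.1), and Visit 1 records whether the participant is in ICU, in hospital outside ICU, or an outpatient (Section 6.1.1).

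**Severity and time.** Section 7.1 takes the worst level of care that a participant received as the severity variable for the primary analysis. The same section hypothesizes that immune responses change in the course of infection.

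**Comparisons.** Section 7.4.2 will "summarize data by group, time point, gender, and race, for example". Two groups are compared with a Wilcoxon rank sum test. More than two are compared with a Kruskal-Wallis or F-test, with pairwise tests to follow: "Should the overall test reach statistical significance at the 2-sided 0.05 level". Adjusted comparisons use "multiple linear regression to compare groups while adjusting for potential confounders (e.g., age, gender, race, comorbidities") and, for response rates, "binary logistic regression to adjust for potential confounders (e.g., age, gender, race, comorbidities"). For repeated measurements: "Longitudinal data will be analyzed using statistical methods for repeated measures and dependent data". The time scale of those models is not stated.

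**Signatures.** "Some of the primary and secondary analyses will seek to identify predictive signatures of categorical outcome variables (e.g., disease severity"). The events given as examples are progression and hospitalization. The laboratory predictors include viral load and immune responses, and performance is assessed by nested cross-validation.

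**The concern.** The protocol's own hypothesis is that responses depend on the day of illness. At Visit 1 that day is uncontrolled, and severity is defined by level of care, which is tied to where a patient is recruited and may be tied to when. If inpatients and outpatients enter at different DPO, a Visit 1 difference between care levels can reflect time since onset instead of severity. Neither the rank tests nor a regression on age, gender, race and comorbidities would remove it.

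Visit 1 matters because it supplies the early blood. Table 2 lists no serum or PBMC phlebotomy at Visit 2 (DPO 7), so the next scheduled adult draw is at DPO 15, and the next scheduled serum draw in children is at DPO 30.

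The signature models raise a separate question of order. If a participant is already in hospital when the sample is taken, viral load or an immune response in that sample cannot predict the hospitalization. It may instead reflect the illness that caused admission, or the care that followed it.

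**Working it through.** The protocol states no figure on this point, and the power tables in Section 7.2 are unfilled templates, so there is nothing to reproduce. The size below is an illustration.

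**1. Which samples are affected.** Table 2 lists six adult serum draws (Visit 1 and DPO 15, 30, 90, 180, 365). Five of the six carry a DPO label. Children have four (Visit 1 and DPO 30, 90, 365), of which three carry one. The problem is confined to Visit 1 and to analyses that include it.

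**2. Size of a spurious difference.** Suppose that severity has no effect, that the response rises by *b* SD per day, and that mean DPO differs by *g* days between two care levels. The expected difference is δ = *b* × *g*. With *n* per group, SD 1 and a two-sided 0.05 level (the level in Section 7.4.2), the chance of a false positive is

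P = Φ(δ/√(2/n) − 1.96) + Φ(−δ/√(2/n) − 1.96).

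- No gap: δ = 0, so P = 2 × Φ(−1.96) = 5%.
- *n* = 100, *b* = 0.10, *g* = 2: δ = 0.20, √(2/100) = 0.141, ratio 1.41, P = 29%.
- *n* = 100, *b* = 0.15, *g* = 4: δ = 0.60, ratio 4.24, P = 99%.

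Assumptions: *b* from 0.05 to 0.15, *g* of 2 or 4 days, *n* of 50 or 100. None of these is in the protocol.

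**3. Simulation of the tests named in Section 7.4.2.** There was no true severity effect, residual SD was 1, DPO had SD 3 within each group, and each row had 1,500 runs. Entries are the percentage of runs with p < 0.05.

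| n per group | slope (SD/day) | gap (days) | Wilcoxon | regression on age | regression on age and DPO |
|---|---|---|---|---|---|
| 50 | 0.05 | 2 | 7.4 | 7.3 | 4.7 |
| 50 | 0.05 | 4 | 14.1 | 15.0 | 4.8 |
| 50 | 0.10 | 2 | 12.3 | 13.5 | 4.1 |
| 50 | 0.10 | 4 | 45.8 | 46.7 | 5.5 |
| 50 | 0.15 | 2 | 24.3 | 24.4 | 5.8 |
| 50 | 0.15 | 4 | 74.9 | 76.5 | 5.3 |
| 100 | 0.05 | 2 | 9.8 | 9.7 | 3.6 |
| 100 | 0.05 | 4 | 25.7 | 26.9 | 4.4 |
| 100 | 0.10 | 2 | 24.4 | 25.6 | 4.3 |
| 100 | 0.10 | 4 | 74.1 | 76.9 | 4.3 |
| 100 | 0.15 | 2 | 47.0 | 48.2 | 4.3 |
| 100 | 0.15 | 4 | 96.5 | 96.5 | 4.4 |

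The rates are a little below those of step 2 because the spread of DPO adds to the total SD: √(1 + 9*b*²) = 1.04 at *b* = 0.10. Adjusting for age does not help. Adding DPO brings the rate to between 3.6% and 5.8%.

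**4. Signature models.** No arithmetic is needed. Section 6.1.1 admits participants who are already in hospital or in ICU. Section 7.4.2 models hospitalization from laboratory variables and sets neither a rule that the sample precede the event nor a restriction to participants still at risk. A post-event sample is therefore permitted. Nested cross-validation guards against overfitting, but each fold contains the same post-event samples, so the bias passes through it. This step needs no assumption about DPO.

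**The case against.** The strongest reply is that the plan does attend to time. Onset date is collected in order to derive DPO, all scheduled follow-up visits are labelled by it, summaries are by time point, and repeated-measures models are planned. Section 4 also says that the association of duration of illness with immune responses will be explored. A reader might infer that the plan disregards when samples were taken. The documents do not support that.

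Both adjuster lists are examples, Section 7.4 calls itself an overview, and a statistical analysis plan that is not shown could add DPO. This stands as a limit: nothing in the protocol excludes DPO. It does not dispose of the point. The tests named for group comparisons adjust for nothing, and the examples that the protocol chose leave out the variable that its own hypothesis makes central.

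A reader might also infer that hospital patients will be sampled later, so that false severity findings are to be expected. The protocol gives no DPO distribution by care level, and for an unnamed pathogen both the direction and the size of any gap are unknown.

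Finally, classifying severity from concurrent samples is legitimate, and progression can follow the sample. The protocol does not say that post-event samples will be used. It fails to rule them out, and the problem is clearest for hospitalization.

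**Conclusion.** The point holds in two limited parts.

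First, Visit 1 comparisons across care levels are not aligned on DPO, and DPO is not named as an adjuster. If care levels enter at different DPO, severity is confounded with time since onset. The size in this study is unknown, and it is nil if there is no gap. In the illustration, false-positive rates run from 5% with no gap (by formula) to 96.5% in the most extreme simulated setting, and from 3.6% to 5.8% with DPO in the model. These figures rest on assumed slopes, gaps, SDs and group sizes. The recovery also assumes that the model has the right shape for DPO (linear in the simulation) and that the DPO ranges of the care levels overlap.

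Second, the hospitalization and progression models permit predictors sampled after the event, which cross-validation cannot correct. This follows from the text alone.

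The protocol should be changed on both parts. Comparisons confined to the DPO-labelled follow-up visits are largely outside the concern.

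**What to change.** Amend Section 7.4.2 as follows.

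- For Group 1, use actual DPO at sampling, as a covariate or as the time axis (a spline or preset windows), in every age and severity analysis that includes Visit 1 samples.
- State that unadjusted Visit 1 differences across care levels will not be interpreted as severity effects.
- Fit prediction models for hospitalization or progression only in participants not yet at that level of care at sampling, and only with samples taken before the event.
- Label any model that uses concurrent or later samples as classification of severity, not prediction.

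The Group 1 part needs no new data, because the onset date is already collected. It is limited to Group 1 because the Group 2 baseline list in Section 4 does not name symptom onset date. The cost is a change of wording, and fewer participants and events in the prediction analysis.
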